## Stopping Rule

For safety reasons, we propose to temporarily suspend enrollment and review with our DSMB if any two subjects experience the following despite dose reduction:

A single occurrence of venous methemoglobin level >5%
 If subjects report change in skin tone and dizziness or other signs of methemoglobinemia for ≥24 hours, an interim visit will be scheduled (if not already being seen for a research visit) and the following steps will occur. The visit can be conducted in UPMC Presbyterian or the TRC.

The physician investigator will factor relevant subject symptoms and hemodynamics and:

- Determine if unblinding is needed (if methemoglobin % >5) and,
- If subject is willing to do an interim visit with repeat drug dosing of 20 mg with follow up methemoglobin and BP pressure monitoring or
- Subject should be withdrawn

Interim visit: If methemoglobin is greater than 5%, the PI will be unblinded to drug or placebo assignment. If subjects are on nitrite, subjects will be asked to repeat drug dosing of 20 mg sodium nitrite with follow up methemoglobin and hemodynamic monitoring. A study physician or PI will evaluate data and make a determination regarding discharge on 20 mg tid. If discharged on 20 mg tid, subjects will be contacted via phone for the next 2 days for symptom re-assessment. If symptoms remain resolved, subjects will continue on 20 mg tid. If symptoms persist, subjects will be requested to come in for repeat

methemoglobin testing after 3 days. If level persists above 5% on lower dose, participation in the study for the subject will be discontinued.

- Blood pressure (BP) and related symptoms: If subjects experience lightheadedness or dizziness, we request that they call the study coordinator who will assess their symptoms, compare to baseline levels, and discuss need for interim visit with study physician. If a visit is indicated, BP, RR, heart rate, pulse co-oximetry and methemoglobin level via co-oximetry will be measured.
  - If systolic BP ≤ 90mm Hg, the study drug will be reduced from 40 TID to 20 TID. Subjects will be reassessed via telephone to ensure that the patient is stable on the new dose. If stable and asymptomatic, subjects will continue with the half dose.
  - If subjects are symptomatic with dizziness, lightheadedness for ≥ 24 hours, and require fluid replacement or other therapy for hypotension, subjects will be requested to return to clinic for an interim visit for assessment of vitals, methemoglobin percent, and evaluation by an investigator-physician to reevaluate the subject's suitability for continued participation based on symptoms.
  - If SBP remains ≤ 90mm Hg and symptomatic and at the lowest dosage of 20mg TID, subject will be withdrawn.

If an unexpected fatal event or any of the above life-threatening events occur despite dose reduction, the study will be halted, until data review by investigators and the Data Safety Monitoring Board has rendered a final recommendation about study continuation.

Other potential reasons for stopping participation in study activities

- 1. Subject participation will be discontinued if a participant has a positive pregnancy test at any point during study participation.
- 2. In the event that the medication compliance rate is < 80%, subjects will be reeducated on medication compliance. If medication compliance falls outside of the acceptable range more than 2 times, the study investigators will discuss subject eligibility for continued participation in the study.

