#### Nitrite:

Sodium nitrite has been used commercially as a food preservative, an anti-corrosive agent, a coloring agent, and an anti-anginal agent, with additional uses in laxatives, burn ointments, and liniments. Amyl nitrite has been inhaled or ingested as an euphoric stimulant. Nitrite has also been found as a contaminant in well water. Literature searches generated case reports of nausea, vomiting, abdominal pain, dizziness, headache, flushing, cyanosis, tachypnea, dyspnea, hypotension, and death attributed to excess nitrite (high-dose) exposure from these sources as a consequence of methemoglobinemia due to oxidation of heme-iron in oxyhemoglobin. Normal background methemoglobin production is 1-3%. If levels of methemoglobin rise above approximately 30% of total hemoglobin, a subject may appear cyanotic and experience dyspnea, due to the reduced oxygen carrying capacity of hemoglobin

(methemoglobin cannot bind oxygen). Levels above 50% can cause seizures, hypotension, coma, and death. Sodium nitrite administration for cyanide poisoning at the labeled dosage of 300 mg causes methemoglobinemia, a desirable effect, as methemoglobin binds to cyanide, thus protecting cellular mitochondria. A standard dose of nitrite used for cyanide poisoning is 300 mg up to 600 mg. Note that methemoglobin levels have never risen higher than 3% at the currently used therapeutic doses (< 75 mg) in 80 volunteers in phase I studies at the NIH.

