The Sponsor of this study proposal, [name], has previously held an IND for sodium nitrite (IND # 70,411) for cardiovascular applications and currently has an approved IND for the use of sodium nitrite for lung transplant recipients (IND # 111,643). The cardiovascular IND involved the administration of sodium nitrite to 69 normal volunteers in 4 phase I-II clinical trials without observed adverse effects. He has also treated 11 subjects with sickle cell disease on this IND without observed adverse effects. The lower doses of nitrite used in these investigational treatment regimens – 60-120 mg daily or 20-40% of the dose (300mg) used in the emergency treatment of cyanide poisoning – do not produce methemoglobin levels greater than 3% and have not been associated with clinically significant hypotension. There have been no adverse events noted in the 80 treated normal human volunteers and patients with sickle cell disease. In another study by [name] et al., 18 healthy adults received an infusion of sodium nitrite totaling 75 mg (15 minutes each x 2 infusions). This was associated with a 7 mmHg decrease in mean arterial pressure, a peak methemoglobin of less 3%, and no other significant effects. Note this single dose is 1.9 times the single dose per time of day we plan to use in this trial.

In an open-label three-way crossover study, 9 healthy adult subjects received two single high dose oral sodium nitrite aqueous solutions (0.12 and 0.06 mmol NaNo2/mmol Hb, equivalent to 290-380 mg and 140-190 mg sodium nitrite, respectively, depending on the total body hemoglobin level of the person) and one intravenous sodium nitrite dose (0.12 mmol NaNo2/mmol Hb). Note that this is 1.2-3.2 times the daily dose we plan to use in this trial. There was a washout period of at least 7 days between each of the treatments. Mild headache occurred in 44-55% of subjects and was the most frequent complaint during each treatment session, which the authors ascribed to the sodium nitrite, not methemoglobinemia, as the percentage of methemoglobinemia stayed below clinically toxic levels (<15%). By report, up to 22% experienced nausea, which subsided within half an hour. The pharmacokinetic analysis of this study indicated similar bioavailability of oral and IV delivery of nitrite, as well as similar side effect and safety profiles.

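### The stopping rule requires an interim visit for signs of methemoglobinemia only after 24 hours, which is too slow for a change in skin tone

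*Combined protocol and SAP*

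**What the plan says.** The methemoglobin item of the Stopping Rule (protocol 5.5.2) reads: "If subjects report change in skin tone and dizziness or other signs of methemoglobinemia for ≥24 hours, an interim visit will be scheduled". The steps that follow depend on the reading at that visit: "If methemoglobin is greater than 5%, the PI will be unblinded to drug or placebo assignment". A subject found to be on nitrite is then re-dosed at 20 mg under observation, and participation ends if the level stays above 5% on the lower dose. The item gives no time limit for the visit and no dosing instruction for the period before it.

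The blood pressure item of the same rule has a quicker route. A subject with dizziness or lightheadedness calls the coordinator, with no minimum duration. The need for a visit is then discussed with a study physician: "If a visit is indicated, BP, RR, heart rate, pulse co-oximetry and methemoglobin level via co-oximetry will be measured". At a systolic pressure of 90 mmHg or lower, "the study drug will be reduced from 40 TID to 20 TID", also without a duration condition. A later item brings the 24 hours back: "If subjects are symptomatic with dizziness, lightheadedness for ≥ 24 hours, and require fluid replacement or other therapy for hypotension". Those subjects are asked to attend so that their suitability to continue can be reviewed.

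Section 2.2.3 is more general. It encourages immediate contact about new symptoms and prompt return to clinic for particular concerns, and it adds weekly calls with symptom review.

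On the risk itself, 5.1 states: "If levels of methemoglobin rise above approximately 30% of total hemoglobin, a subject may appear cyanotic and experience dyspnea". Above 50% it lists seizures, hypotension, coma and death. It also reports that "methemoglobin levels have never risen higher than 3% at the currently used therapeutic doses (< 75 mg".

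**The concern.** The rule written for this particular risk is slower than the general advice in 2.2.3. A coordinator who follows the specific rule could reasonably wait 24 hours before arranging a visit for a subject whose skin color has changed. By 5.1, a color change caused by methemoglobin points to a level well past the one at which the protocol wants action. Unblinding, the 20 mg re-dose and withdrawal all wait for the reading.

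Signs that clear within 24 hours never trigger a required reading under this item. The trial-level rule is affected as well. It suspends enrollment when two subjects exceed 5% despite dose reduction, so it can count only levels that are measured.

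**Working it through.** There is no stated figure for the 24-hour condition to reproduce, so the check compares the routes to a reading and then does simple arithmetic.

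**1. Routes to a methemoglobin reading**

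| Route | Minimum duration | Visit | Reading |
|---|---|---|---|
| Methemoglobin item, Stopping Rule | 24 h | Required, no deadline | At the visit |
| Dizziness call, Stopping Rule | None | If judged indicated | If a visit takes place |
| Hypotension needing therapy, Stopping Rule | 24 h | Requested | At the visit |
| Contact and return, 2.2.3 | None | For particular concerns | Not named for this unscheduled return |
| Weekly call, 2.2.3 | None | No | No |
| AE follow-up, 5.5.2; investigator discontinuation, 2.7 | None | Judgment | Not named |

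No row requires a reading on first report of a change in skin tone.

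**2. Sign level against action level.** Inputs are about 30% (5.1) and 5% (Stopping Rule). 30 / 5 = 6. This applies only if the color change is due to methemoglobin; 5.1 also lists flushing as a rare effect of nitrite.

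**3. Exposure during the wait.** Dosing is 40 mg three times daily (2.2.1). 24 h = 3 dose times; 3 × 40 mg = 120 mg. This assumes a nitrite period and continued dosing. If 2.2.3 is acted on at once, the figure can be 0. It is not a ceiling, because the visit has no deadline and each further 24 h would add 120 mg on the same assumptions. The protocol gives no basis for choosing a delay, so I put no weight on larger totals.

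**4. How likely the event is (5.1)**
- Doses below 75 mg: at most 3%. 3 / 30 = 0.1 of the sign level.
- Regimens of 60–120 mg daily: not above 3%. The planned daily dose is 3 × 40 = 120 mg, the top of that range.
- 48-hour infusions: dose-limiting toxicity was confined to asymptomatic blood pressure falls and asymptomatic levels above 5%. The protocol puts that dose at 8.2 times the planned daily dose. Its own inputs give 10.6 mg/kg/day × 95 kg = 1,007 mg/day, and 1,007 / 120 = 8.4, which is close enough.
- Single oral doses of about 140–380 mg: below 15%. 140 / 40 = 3.5 and 380 / 40 = 9.5 times the planned single dose.
- Supervised readings follow the first randomized dose (2.3.2, Randomization) and the crossover dose (2.3.3, Cross-Over Visit), so every subject who crosses over has a reading at the start of the nitrite period.

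None of these is ten weeks of three-times-daily home dosing in PH-HFpEF.

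**5. Effect of pausing doses.** One period has 70 days × 3 = 210 doses. If 1 to 3 doses are held (an assumption), 1 / 210 = 0.5% and 3 / 210 = 1.4%, far from the 80% compliance threshold in 2.2.4.

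**The case against.** The strongest reply is that the plan already allows same-day action. Subjects are told to make contact at once, are phoned weekly, and may be brought in promptly. The skin-tone trigger is paired with dizziness, and dizziness has its own call with no waiting time. On that view the 24 hours is a backstop: a visit becomes compulsory then, and earlier review stays open.

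Much of this stands. A reader might infer that the protocol forbids or fails to provide for a visit before 24 hours; it does neither, and the two sections differ in speed without contradicting each other. What remains is that the early visit is discretionary and that a color change without dizziness has no mandatory early reading.

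Three other inferences go too far:
- **That the reassuring data are all single-dose.** Section 5.1 also reports daily regimens up to this trial's dose, and 48-hour infusions.
- **That several days of dosing would build up to a dangerous level.** No visit delay is stated, and nothing in the protocol shows accumulation across doses.
- **That the hypotension item delays acute care.** Those subjects are already receiving therapy and have the no-wait call; the visit reviews whether they should continue.

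**Conclusion.** The point holds in a limited form. For a change in skin tone, and for other signs that may be methemoglobinemia, the Stopping Rule makes a visit mandatory only after 24 hours, with no deadline and no dosing instruction. Against a possible level six times the action threshold, three dose times (120 mg) is too long to wait for a required reading.

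This rests on three conditions: the sign is caused by methemoglobin, the subject is in a nitrite period, and dosing continues. The event is unlikely on the protocol's own evidence, and no endpoint or analysis is affected. Even so, the rule exists for the exceptional subject, and a small wording change would serve that subject better.

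**What to change.** Amend the methemoglobin item of the Stopping Rule in 5.5.2:

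- Delete the 24-hour condition for new cyanosis or skin-tone change, and for new or clearly worsened signs that a study physician judges may be methemoglobinemia. The physician's judgment matters because exertional dyspnea is a qualifying symptom here and headache is non-specific; pausing drug for every such complaint would trigger too often.
- On first report, the subject calls the team and takes no further dose until a study physician has advised.
- Measure methemoglobin as soon as possible, the same day where feasible, and record the time of the last dose.
- Above 5%, follow the existing steps. At 5% or less, the study physician decides on resumption, allowing for the time since the last dose, because a low level after a held dose is only partly reassuring.
- Apply this identically in both arms, so that the pause does not unblind, and cross-refer to 2.2.3. The hypotension item needs at most the same cross-reference.

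Interim visits and co-oximetry are already in the plan. The cost is some extra unscheduled visits at $25 plus parking each (7.2) and a few held doses. As an illustration and not a bound, one extra visit per subject in each period would be 26 × 2 × $25 = $1,300 plus parking.

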## 2.2.3. Safety Monitoring:

Weekly phone follow-up (+/- 7 days) assessments will occur while on active study treatment (when subjects are not followed up in clinic) that will include symptom review, assessment of adverse events, review of concomitant medications, and interval histories. Subjects may return to clinic for outpatient assessments at weeks 4 and 8 (both Arm 1 and Arm 2) if the PI deems it necessary to bring the patient in for an evaluation. No weekly phone follow up may be necessary if subjects are evaluated in clinic. Clinical visits are completed in the outpatient clinics at UPMC Presbyterian outpatient cardiology and/or Falk Clinic, Comprehensive Lung Center, or Translational Research Center (TRC). The in-person clinical visits include a brief physical exam, NYHA functional class assessment, vital signs including oxygen and methemoglobin levels via co-oximetry, NTproBNP lab, 6MWT and Borg scale, interval histories, medication compliance review, AE assessment/symptom review, and dispensing of study drug.

In addition to these formal evaluations, subjects will be encouraged to immediately contact the study investigator and/or the study coordinator with questions, concerns, or to report new symptoms that occur during their study participation. If there are particular concerns that need to be addressed sooner than the in-person visits, the subject will be asked to return to the clinic as soon as possible for evaluation. If appropriate, based upon the evaluation, medical treatments will be provided to subjects, including appropriate referral to physicians or other services at the UPMC.

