## 2.3.6. Schedule of Assessments

The table below summarizes the protocol procedures that will be performed throughout the study trial TABLE 1

TABLE 1										
Study Phase	Screening	Baseline	Weekly Phone Call +/- 7 days	Weeks 4 and 8 (per Pl only) +/- 7 days	Week 10 +/-14 days	Cross- over Visit	Weekly Phone Call +/- 7 days	Weeks 4 and 8 (per Pl only) +/- 7 days	End of Treatment (EOT)	Follow-up Period Phone Call
Informed Consent	X									
I/E Criteria	X									
Medical History &	Х									
Demographics	v			V	v	V		V	V	
Physical Exam	X	Х		X	X	X		X	X	
Vital Signs & Body Weight		Χ								
Oxygen Saturation	X			X	X	X		X	X	
Blood Samples: fasting glucose, CMP, hemoglo bin A1C, fasting lipid profile, PT/PTT, complete blood count, platelet and differential, research labs	X				х	X			х	
α NTproBNP blood test	Х			Х	Х	Х		Х	Х	
Urine Pregnancy test (if applicable)	X				X	X			x	
NYHA functional class assessment	Х			X	X	X		х	X	
α 6 minute walk test (6MWT)	Х			Х	Х	Х		Х	Х	
Echocardiogram	X∞				Х				х	
Spirometry lung	X.	Х							Α	
function test										
Incremental exercise testing (IET)		Х								
Practice Constant Work Rate (CWR P )		Х								
Constant Work Rate (CWR) test		Х			Х	Х			Х	
(RHC): RA, RV, PA, PCWP, CO/CI Resting hemodynamics and (sub-maximal exercise at Week 10 and EOT only)	Χ †				х				Х	
Micromanometry     (optional)	X				X				X	
Accelerometer		Х			Х	Х			Х	
л IVGTT					Х				X	
MetHgb levels via co-	Х	Х		Х	Х	Х		Х	X	
oximetry		v								
Randomization Dispense and study		X		X	Х	Х		X	If patient wants to	
drug administration		^							continue open label	
Study drug compliancy assessment				Х	Х			Х	X	
Dispense subject diary		Х		Х	Х	Х		Х	Х	
α KCCQ, SF-36 and PAH-SYMPACT questionnaires		Х			Х	Х			Х	
AE Assessment			Х	Х	Х	Х	Х	Х	х	Х
Review of concomitant medications	Х		X	X	X	X	X	X	x	
Interval History Assessment			Х	Х	Х	Х	Х	Х	Х	Х

- Sponsor: [name]
- ∞ If subject has had an echocardiogram within the past year, we may not obtain during screening.
- Spirometry lung function test may not be needed at baseline visit if results are available within 6 months from enrollment.
- ↑ A screening RHC may not be performed if a RHC was completed within 12 months from enrollment per PI discretion.
- 3 Micromanometry is optional and completed during RHC.
- n Insulin-dependent diabetics will not receive the IVGTT.

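### A subject stepped down to 20 mg TID for methemoglobin above 5% needs no level on the sustained lower dose unless symptoms persist

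*Combined protocol and SAP*

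**What the plan says.** The rule is in the interim-visit text of the Stopping Rule, section 5.5.2. When methemoglobin exceeds 5%, the PI is unblinded. If the subject is on nitrite, "subjects will be asked to repeat drug dosing of 20 mg sodium nitrite with follow up methemoglobin and hemodynamic monitoring". Then "A study physician or PI will evaluate data and make a determination regarding discharge on 20 mg tid"; no numeric limit is given for that decision.

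After discharge, the subject is phoned over the next 2 days about symptoms, and the path splits:

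- Symptoms gone: "If symptoms remain resolved, subjects will continue on 20 mg tid". No further level is specified.
- Symptoms present: "If symptoms persist, subjects will be requested to come in for repeat" methemoglobin testing after 3 days.

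The individual stopping criterion follows directly: "If level persists above 5% on lower dose, participation in the study for the subject will be discontinued". At trial level, enrollment is suspended if two subjects, despite dose reduction, meet a criterion such as "A single occurrence of venous methemoglobin level >5"%.

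Nothing elsewhere in the body text fills the gap for a subject without symptoms. The weekly calls in section 2.2.3 cover "symptom review, assessment of adverse events, review of concomitant medications, and interval histories". Section 2.3.3 and Table 1 make weeks 4 and 8 phone contacts, with a clinic visit and a level only if the PI asks for one. The next level required of everyone is at Week 10 (first period) or End of Treatment (second period). The Protocol Synopsis differs: it still describes weeks 4 and 8 as in-person visits that include a methemoglobin level.

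**The concern.** The protocol sets a numeric limit of 5% and then lets symptoms decide whether the limit is checked on the regimen the subject will actually take. A level on the lower dose does exist, because one is taken after the 20 mg dose at the interim visit, and the discontinuation criterion can be applied to it. But it follows a single dose, and nothing requires confirmation under repeated dosing three times a day.

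Resolution of symptoms is some evidence that the level has fallen, particularly as these subjects usually enter the pathway with symptoms. It does not show that the level is below 5%.

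Two things are at stake. A subject already shown to exceed 5% on 40 mg could stay above the limit on 20 mg TID for weeks without anyone knowing. And the two-subject suspension rule, which counts venous levels above 5% after dose reduction, can miss a qualifying event until Week 10 or End of Treatment if subjects who feel well are not sampled.

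**Working it through.** No power or sample-size figure is involved. The check compares the sections and counts days.

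**Can a level above 5% occur without symptoms?** Section 5.1 bears on this in two places.

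- A 48-hour intravenous study in 12 volunteers reports rises above 5% with no symptoms. The protocol puts that dose at 8.2 times the trial's daily dose. Against the reduced regimen it is 8.2 × 120 mg ÷ 60 mg = 16.4 times. The study shows that symptoms and the 5% limit can part company; it does not show how often this happens on 20 mg TID.
- Cyanosis and dyspnea are placed at about 30% of total hemoglobin, well above the limit.

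**Does another rule require a level sooner?**

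| Provision | Requires a level on sustained 20 mg TID? |
|---|---|
| Post-dose checks at screening and first study dose (2.3.1, 2.3.2) | No; both come before the step-down |
| Two days of calls after discharge (5.5.2) | No; symptoms only |
| Weekly calls (2.2.3) | No |
| Weeks 4 and 8 (2.3.3, Table 1) | Only if the PI calls the subject in |
| Following adverse events to outcome (5.5.2) | No level named |
| Week 10 / End of Treatment (2.3.3) | Yes |

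**How long is the gap?**

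Inputs: a 70-day treatment period and 3 doses per day. The visit window is ±14 days (2.3.3), so the level falls on day 56, 70 or 84. Assume no PI-directed visit.

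Gap = day of the next required level − day of step-down. Doses = 3 × gap.

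| Step-down | Early (day 56) | Nominal (day 70) | Late (day 84) |
|---|---|---|---|
| Day 2 | 56 − 2 = 54 days, 162 doses | 70 − 2 = 68 days, 204 doses | 84 − 2 = 82 days, 246 doses |
| Day 28 | 28 days, 84 doses | 42 days, 126 doses | 56 days, 168 doses |
| Day 56 | 0 days, 0 doses | 14 days, 42 doses | 28 days, 84 doses |

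If the synopsis wording governed, a day-2 step-down would be followed by a level at week 4: 28 − 2 = 26 days (78 doses), or 35 − 2 = 33 days (99 doses) at the late end of the ±7-day window.

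With a mandatory level after 3 days, the first reading on the sustained dose comes after about 3 days, or 3 × 3 = 9 doses, whenever the step-down occurs.

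**The case against.** The case on the other side concerns importance; the text and the day counts are not in dispute.

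- **Rarity.** Section 5.1 reports no level above 3% at doses under 75 mg in 80 volunteers. If they were representative, which is an assumption, the one-sided 95% upper bound for 0 of 80 is 1 − 0.05^(1/80) ≈ 3.7%. That is 0.037 × 26 ≈ 0.96, fewer than one of the 26 subjects exceeding even 3%. This stands as a reason to expect few cases. It says less about a subject already above 5% on 40 mg, who has departed from that experience.
- **Low toxicity.** Single oral doses of 290–380 mg, which are 14.5 to 19 times 20 mg, kept levels below 15%, described in section 5.1 as below clinically toxic. This stands: serious harm is unlikely. The limit the protocol chose is nevertheless 5%.
- **Symptomatic entry.** A subject who had symptoms near 5% may well notice a recurrence. This is fair, and it weakens the concern for such subjects. It does not cover someone whose raised level is found at a routine visit.
- **Conservative re-dose.** The 20 mg dose may be given on top of recent 40 mg dosing, so its level could overstate what sustained 20 mg TID produces. This is plausible, but the protocol states no interval before the re-dose, so it remains an inference.
- **Informed discretion.** The PI is unblinded, knows the case and may recall the subject. This mitigates the gap but does not require a level.
- **What the fix leaves.** For a day-2 step-down, 51, 65 or 79 days would still separate the 3-day level from the next required one (54, 68 or 82 minus 3). That is correct. The gain is one confirmed level on the sustained regimen, not continuous monitoring.

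**Conclusion.** The concern holds. A subject on nitrite who exceeds 5%, is discharged on 20 mg TID and feels well can continue on the evidence of one single-dose level until Week 10 or End of Treatment.

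The unmeasured interval is 68 days in the nominal worst case, shorter for later step-downs, and can be zero for a step-down at week 8. These figures assume that the body text and Table 1 govern rather than the synopsis, and that the PI calls no extra visit. They measure time without a reading, not the probability of harm. The documents do not give the probability of a level above 5% on sustained 20 mg TID.

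With few affected subjects and low expected toxicity, this is a correction worth making rather than a serious defect. The limit, the test and its timing are already in the protocol; only the condition attached to the test is wrong.

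**What to change.** In the interim-visit text of the Stopping Rule, require the existing repeat methemoglobin level after 3 days for every subject discharged on 20 mg TID, whatever the symptoms. Use co-oximetry, with a blood sample if the device cannot read, as section 2.4.7 already allows. Confirm any reading above 5% with a venous sample, because the two-subject suspension rule counts venous levels. Apply the existing above-5% discontinuation criterion to the result; no new threshold is needed.

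The cost is one wording change and one short extra visit with a non-invasive reading for each subject stepped down. Blood is needed only when the reading exceeds 5% or cannot be obtained.
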